### **Type of Participant and Disease Characteristics**

2. Are participants with histologically or cytologically confirmed locally advanced or metastatic BTC.
3. Availability of tumor (primary or metastatic) archival material or fresh biopsies is mandatory. Fine needle aspirates, transductal aspirates, or cell blocks are not acceptable. Endoscopic retrograde cholangiography or intraductal ultrasounds assisted biopsy is acceptable, needle or excisional biopsies, or resected tissue, are preferable. Tumor biopsies and tumor archival material must be suitable for biomarker assessment as described in the Laboratory Manual.
4. Participants with BTC must have failed or be intolerant to 1L systemic platinum-based chemotherapy administered for locally advanced or metastatic disease. Only one prior treatment line is allowed. Participants who received adjuvant platinum-based chemotherapy and had evidence of disease recurrence within 6 months of completion of the adjuvant treatment are also eligible. If recurrence occurs during or within 6 months after the adjuvant chemotherapy, adjuvant platinum-based chemotherapy is counted as 1L chemotherapy.
5. Disease must be measurable with at least 1 unidimensionally measurable lesion by RECIST 1.1 and verified independently by IRC.
6. Eastern Cooperative Oncology Group (ECOG) PS of 0 to 1 at study entry and Day 1 of treatment with M7824.

7. Life expectancy  $\geq$  12 weeks as judged by the Investigator.
8. Adequate hematological function defined by white blood cell count  $\geq 3 \times 10^9/\text{L}$  with absolute neutrophil count  $\geq 1.5 \times 10^9/\text{L}$ , lymphocyte count  $\geq 0.5 \times 10^9/\text{L}$ , platelet count  $\geq 75 \times 10^9/\text{L}$ , and hemoglobin (Hgb)  $\geq 9 \text{ g/dL}$ .
9. Adequate hepatic function defined by a total bilirubin level  $\leq 1.5 \times$  upper limit of normal (ULN), an aspartate aminotransferase level  $\leq 2.5 \times$  ULN, and an alanine aminotransferase (ALT) level  $\leq 2.5 \times$  ULN. For participants with liver involvement in their tumor, aspartate aminotransferase  $\leq 5.0 \times$  ULN and ALT  $\leq 5.0 \times$  ULN is acceptable.

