### Prior/Concomitant Therapy

15. Participants who are not eligible for or have not been treated with 1L systemic chemotherapy will be excluded.

---

- 16. Systemic anticancer treatment after failing 1L platinum-based chemotherapy.
- 17. Concurrent treatment with nonpermitted drugs.
- 18. Prior participation in a M7824 clinical trial.
- 19. Prior therapy with other immunotherapy or checkpoint inhibitors, such as anti-PD-1, anti-PD-L1, anti-cytotoxic T-lymphocyte-associated antigen-4 (CTLA-4) antibodies.
- 20. Prior therapy with any antibody or inhibitors targeting the TGF- $\beta$ /TGF- $\beta$  receptor pathway.
- 21. Anticancer treatment within 21 days before the start of study intervention, e.g., cytoreductive therapy, radiotherapy involving >30% of the bone marrow (with the exception of palliative bone-directed radiotherapy), immune therapy, or cytokine therapy.
- 22. Anticancer treatment with antibody within 28 days before the start of study intervention.
- 23. Systemic therapy with immunosuppressive agents within 7 days before the start of study intervention; or use of any investigational drug within 28 days before the start of study intervention.
- 24. Vaccine administration within 4 weeks of M7824 administration. Vaccination with live vaccines while on study is prohibited. Administration of inactivated vaccines is allowed (e.g., inactivated influenza vaccines).

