### 9.2 Sample Size Determination

The study aims at demonstrating an  $\text{ORR} > 10\%$  in the intention-to-treat (ITT) population by means of an exact binomial test.

The planned total sample size is 141 participants based on the following assumptions:

1. ORR of 18%
2. Alpha = 0.025 (1-sided) for the Exact test of the null hypothesis of an  $\text{ORR} \leq 10\%$ .

Under the given assumptions, the power to reject the null hypothesis at the primary analysis (PA) is 80%.

An observed ORR of 15.6% (22/141) would achieve a positive ORR outcome and would lead to an exact 95% CI of (10%, 22.7%).

The 2-sided 95% Clopper-Pearson CIs for different observed values for the ORR are provided in [Table 8](#).

**Table 8** Confidence Intervals for Different Objective Response Rates

N	N with CR/PR	ORR (%)	95% CI	
			Lower	Upper
141	15	10.6	6.1	16.9
	20	14.2	8.9	21.1
	21	14.9	9.5	21.9
	22	15.6	10.0	22.7
	25	17.7	11.8	25.1
	30	21.3	14.8	29.0
	35	24.8	17.9	32.8

CI=confidence interval, CR=complete response, N=number of participants, ORR=objective response rate, PR=partial response.

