### Additional Subgroup Analysis Sets

[figure not shown]
Analysis of primary, key secondary efficacy and safety endpoints may be performed on subgroups of interest as specified in this IAP Section 14 and Section 15.1 respectively. Since the study is not powered for any subgroup analysis, all the subgroup analyses are **CCI** in nature.

The following major subgroups will be used for analysis:

- BTC subtype
  - Intrahepatic cholangiocarcinoma
  - Extrahepatic cholangiocarcinoma
  - Gallbladder cancer
- Age group
  - Age < 65 years
  - Age ≥ 65 years
- ECOG PS at baseline
  - ECOG PS 0
  - ECOG PS 1
- Sex
  - Male
  - Female

- Race
  - White
  - Black or African American
  - Asian
  - American Indian or Alaska Native
  - Native Hawaiian or other Pacific Islander
  - More than one race
  - Not collected at the site
  - Other
- Geographic Region
  - Asia
  - US
  - Europe
- Time since completion of 1L platinum-based treatment
  - <6 months
  - $\geq 6$  months
- Disease status at initial diagnosis (based on TNM classification)
  - Locally advanced (M0)
  - Metastatic disease (M1)
  - Unknown (MX)
- PD-L1 expression on tumor cells (TC) and on immune cells (IC) at baseline
  - <1%,  $\geq 1\%$ ; <5%,  $\geq 5\%$ ; <25%,  $\geq 25\%$ ; <50%,  $\geq 50\%$  for TC
  - <1%,  $\geq 1\%$ ; <5%,  $\geq 5\%$ ; <25%,  $\geq 25\%$ ; <50%,  $\geq 50\%$  for IC
  - <1%, 1-<50%,  $\geq 50\%$  for TC
  - <1%, 1-<50%,  $\geq 50\%$  for IC

- ADA status
  - Ever positive
  - Never positive
- nAb status
  - Ever positive (for either assay TGF- $\beta$  or PD-L1)
  - Never positive

For Extrahepatic cholangiocarcinoma participants, following subgroups may also be used for analysis:

- Extrahepatic cholangiocarcinoma subtype
  - Perihilar cholangiocarcinoma
  - Distal cholangiocarcinoma

For ADA and nAb status subgroups, the subgroup analyses will be performed if there are at least 3 ever positive participants.

For all other subgroup variables with more than two categories, any subgroup category with less than 7 participants (approximately 5% of the population) will not be reported in the analysis.

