### 12.4 Previous anticancer treatments and procedures

The previous anticancer treatments and procedures are collected under the “Prior Anti-Cancer Drug Therapies Details” and the “Prior Anti-Cancer Surgeries Details” eCRF pages.

The number of participants in each of the following anticancer treatment categories will be tabulated:

- Participants with at least one type of previous anticancer treatment or procedure (i.e. drug therapy, radiotherapy or surgery)
- Participants with at least one previous anticancer drug therapy
- Participants with at least one previous anticancer radiotherapy
- Participants with at least one previous anticancer surgery

Following details for previous systemic anticancer drug therapy will also be summarized:

- Number of any previous anticancer therapy regimens: 0 / 1 / 2 / 3 /  $\geq$  4
- Number of previous lines of therapy for metastatic/locally advanced disease: 0 / 1 / 2 / 3 /  $\geq$  4 (categories will be data dependent)
- Intent of therapy: Neoadjuvant / Adjuvant / Metastatic or Locally advanced

- Best response of last treatment regimen: Complete Response (CR) / Partial Response (PR) / Stable Disease (SD) / Progressive Disease (PD) / Non-Complete Response/Non-Progressive Disease (non-CR/non-PD) / Not Assessable / Unknown / Not applicable.
- The time since completion of first-line (1L) of platinum-based treatment will also be summarized. Platinum-based treatment will be identified for participants who received at least one platinum-based drug (cisplatin, oxaliplatin or carboplatin) and at least one of the following drugs in the same regimen: gemcitabine, fluorouracil or capecitabine. The time since completion will be measured using the maximum stop date of any of platinum-based drug/gemcitabine/fluorouracil/capecitabine treatment (maximum start date will be used in case the stop date is not available).
- Number of participants per 1L regimen, e.g., cisplatin/gemcitabine, cisplatin/fluorouracil.

Previous anticancer drugs, previous anticancer radiotherapy, and previous anticancer surgery will be presented in separate listings:

- The previous anticancer drug listing will contain participant identifier, age, sex, race, regimen ID, preferred term, medication name, start date, end date, intent of therapy, best response, date of progression.

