#### 14.1.1 Subgroup analysis for BOR

Confirmed BOR, ORR and DCR according to RECIST 1.1 as adjudicated by IRC will also be evaluated on all subgroups as defined in Section 8.2. This will be repeated for Japanese participants including only the ADA and nAb status subgroup.

For ADA and nAb subgroups a listing will present the tumor assessment and overall response per RECIST 1.1 as assessed by the IRC including: participant ID, age, sex, race, ADA Status, nAb PD-L1 Assay Status, nAb TGF- $\beta$  Assay Status, visit, date(s) of imaging, description of target lesions (size, site, status, type, method, response), non target lesions (status, site, method, response), and new lesions (site, status, method), sum of lesion diameters, percent change in target lesions at baseline, and overall response. Two listings will be created: for the ADA positive participants and for nAb positive in either away (PD-L1 and TGF- $\beta$ ) participants.

Participants with missing subgroup category will not be included in the related subgroup analysis. Those subgroups analyses will be supported by forest plots.

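### SAP 12.4 defines first-line platinum treatment more narrowly than eligibility does, and its start-date fallback can only move participants into the ≥6-month subgroup

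*SAP*

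**What the plan says.** **Eligibility.** Protocol 5.1, inclusion criterion 4, says participants "must have failed or be intolerant to 1L systemic platinum-based chemotherapy administered for locally advanced or metastatic disease". It sets no condition on what accompanies the platinum. It also counts adjuvant platinum-based chemotherapy as first line when disease recurs during that treatment or within 6 months after it.

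**Derivation.** SAP 12.4 identifies platinum-based treatment when a participant received cisplatin, oxaliplatin or carboplatin and "at least one of the following drugs in the same regimen: gemcitabine, fluorouracil or capecitabine". Completion is the latest stop date among those drugs, but "maximum start date will be used in case the stop date is not available".

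**Use.** SAP 8.2 lists "Time since completion of 1L platinum-based treatment" as a subgroup variable with two levels, <6 and ≥6 months. SAP 14.1.1, 14.4.2, 14.5.1, 14.6.1 and 14.8.1 apply every section 8.2 subgroup to confirmed response, PFS, DOR, DRR and OS. On absent values, SAP 14.1.1 says: "Participants with missing subgroup category will not be included in the related subgroup analysis". The other four sections carry the same rule.

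**The concern.** Two stated rules affect who enters this subgroup and on which side of the cut.

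First, the SAP definition is narrower than the eligibility criterion, and the SAP gives no reason. An eligible participant whose regimen is not on the SAP list has no completion date and so no category, although the data needed to assign one are collected.

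Second, a start date is not a completion date. Using one in place of the other gives an error of known direction, and no sensitivity analysis covers it. It also differs from the SAP's general approach in section 9. There, missing data are not replaced unless the plan says otherwise. For previous medications, partial end dates are imputed late and wholly missing ones are left missing.

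At stake is a prespecified subgroup reported on five efficacy endpoints. DOR is the most sensitive, since it uses responders only: at the design ORR, 0.18 × 141 ≈ 25 participants across both levels.

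**Working it through.** **1. The design figure, to fix what is not affected.** Protocol 9.2 has N = 141, null ORR 10%, assumed ORR 18%, one-sided alpha 0.025 and power 80%. By the exact binomial distribution:
- P(X ≥ 22 | 141, 0.10) = 0.0239
- P(X ≥ 21 | 141, 0.10) = 0.0419, so 22 is the correct cut-off
- P(X ≥ 22 | 141, 0.18) = 0.8007

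The stated 80% is reproduced. Neither rule in SAP 12.4 enters this calculation.

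**2. The partner-drug rule.** Compare the steps for a participant treated first line with platinum alone or with an unlisted partner:
- Criterion 4: eligible.
- SAP 12.4: no platinum-based treatment identified, so no completion date.
- SAP 8.2: neither <6 nor ≥6 months applies, and there is no other level.
- SAP 14.1.1 and the four matching sections: left out.

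The count k is not in the documents. As illustrations only, k/141 is 2.1% for k = 3, 5.0% for k = 7 and 9.9% for k = 14. Zero is also possible.

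**3. Direction of the start-date error.** SAP 9 measures time since an event back from the first dose and uses 1 month = 30.4375 days. Let T be the true time from completion to first dose. Let G be the time from the latest recorded start to true completion. Then

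derived interval = T + G, with G ≥ 0,

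because the latest start cannot fall after the latest stop. A participant can move from <6 to ≥6 months but never the other way.

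**4. Size of the start-date error.** Misplacement needs T < 6 and T + G ≥ 6, that is 6 − G ≤ T < 6. Exclusion criterion 21 ("Anticancer treatment within 21 days before the start of study intervention") puts a floor under T of about 21 / 30.4375 = 0.69 months. The documents give no first-line duration, so G is an assumption:

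| Assumed gap G | G in months | True intervals misplaced (months) |
|---|---|---|
| 4 weeks (28 days) | 0.92 | 5.08 to <6 |
| 8 weeks (56 days) | 1.84 | 4.16 to <6 |
| 12 weeks (84 days) | 2.76 | 3.24 to <6 |
| 16 weeks (112 days) | 3.68 | 2.32 to <6 |
| 24 weeks (168 days) | 5.52 | 0.69 to <6 (all, given the floor) |

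Everybody moves only if G ≥ 6 × 30.4375 − 21 = 182.6 − 21 = 161.6 days, about 162 days or 23 weeks.

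**The case against.** The case for leaving this alone has four parts.

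- **Few participants may be affected.** Protocol 2.2 names gemcitabine plus cisplatin as standard first-line therapy, and Protocol 4.2 describes the study population as failing that combination. The Schedule of Activities asks sites to record first-line agents and treatment duration, and exclusion criterion 21 makes sites check the time since last treatment. Wholly missing stop dates should be uncommon. This stands: it limits the likely size, though not the error for anyone concerned.
- **The fallback may be narrower than it looks.** The SAP takes the latest stop date across several drugs. On the natural reading, one recorded stop date is enough and the start date is used only when there is none, but the text does not say so. If the partial-date rules in SAP 9 for previous medications also cover prior anticancer drugs, the fallback is confined to wholly missing dates. The SAP does not settle that either.
- **The reach is limited.** SAP 8.2 says the study is not powered for subgroup analyses. Affected participants stay in every main analysis. SAP 12.4 also tabulates first-line regimens and lists prior drugs with their dates, so a careful reader could find the cases. This stands, and it makes the point a correction rather than a threat to the trial.
- **A stronger reading fails.** A reader might infer that the fallback adds the whole regimen length and puts every participant without a stop date in ≥6 months whatever the true interval. The documents do not support this. The date used is the latest recorded start, so the full length is added only if all drugs started together. Moving everyone needs a gap of about 162 days, which neither document states. Criterion 4 also admits intolerant participants, for whom a full course cannot be presumed.

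**Conclusion.** The point holds and should be corrected, at modest priority. Two things follow from the text without any assumption: eligible participants on an unlisted platinum regimen are excluded from this subgroup, and the start-date fallback can only shift participants from <6 to ≥6 months.

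The size cannot be derived. It rests on two unknowns: how many participants had an unlisted regimen or no stop date, and the gap from latest start to true completion. For gaps of 4 to 16 weeks, the lower end of the misplaced range runs from 5.08 down to 2.32 months.

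A reader might also infer that a material share of the 141 is lost, or that the primary result is in doubt. Neither is supported. No count is given, the named standard regimen suggests a low one, and the ORR test, ITT set and power do not use this variable. What is affected is the descriptive summary in SAP 12.4 and one unpowered subgroup on five endpoints.

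**What to change.** In SAP 12.4:
- Identify first-line platinum-based treatment by any platinum drug in the regimen counted as first line, whatever the partner. Include adjuvant therapy that criterion 4 counts as first line.
- Take the latest recorded stop date within that regimen, and state that one recorded stop date is enough.
- If none is recorded, do not use the start date. Class the participant as 'unknown'.
- State whether the partial-date rules in SAP 9 apply to prior anticancer drugs.

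In SAP 8.2, add 'unknown' as a level and show its count and results. Section 8.2 suppresses levels with fewer than 7 participants when a variable has more than two categories, so exempt this level; otherwise the count would disappear. Make clear that 'unknown' is not a missing category under SAP 14.1.1 and the matching sections.

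Use the recorded progression date at most in a sensitivity analysis. Progression may follow completion, which would shorten the interval, and intolerant participants may have no such date.

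The cost is SAP wording and minor programming, since regimen, drug names, dates and progression date are already collected. A few participants move to 'unknown'. Where only some drugs have a stop date, the latest recorded one may still be earlier than true completion, so a small error in the same direction can remain.

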## 12.5 Anticancer Treatment after Discontinuation

Anticancer treatment after discontinuation of study drug will be summarized according to the eCRF page "Anti-cancer Treatment After Discontinuation" for anticancer drug therapy, "Radiotherapy After Discontinuation" for anticancer radiotherapy and to "Surgery After Discontinuation" for anticancer surgery.

The number of participants in each of the following anticancer treatment categories will be tabulated:

- Participants with at least one subsequent anticancer treatment (i.e. drug therapy, radiotherapy or surgery)
- Participants with at least one subsequent anticancer drug therapy
- Participants with at least one subsequent anticancer radiotherapy
- Participants with at least one subsequent anticancer surgery

The type of subsequent anticancer drug therapy as provided in the e-CRF (i.e. Cytotoxic therapy/ Monoclonal antibodies therapy/ Small molecules/ Immunotherapy/ Other) will be described.

In addition, the anticancer treatment after discontinuation of study treatment will be provided in two listings:

- For medication: participant identifier, age, sex, race, preferred term/medication name, medication type, regimen name, intent of therapy, start date and end date.
- For radiotherapy and surgery: participant identifier, age, sex, race, type of therapy, start date, end date, radiotherapy site or name of surgery/location, if radiotherapy total dose and number of fractions, if surgery outcome and was the surgery curative in intent (Y/N)

## 13 Study intervention Compliance and Exposure

*Analysis set: SAF*

Participants will be treated with bintrafusp alfa at a dose of 1200 mg once every 2 weeks, until confirmed progression of disease (PD), death, unacceptable toxicity, study withdrawal, or up to 24 months. This dose will be administered as “flat” doses independent of the body weight.

All dosing calculations below and summaries will be based on “Study Treatment Administration Details” eCRFs page. Data collected during the treatment re-initiation phase will be included in the summary statistics and flagged in the listings.

For the analysis of exposure, a dose is regarded to be administered if the actual dose received is > 0 mg.

Whether the participant re-initiates the treatment or not, the **duration** of treatment of bintrafusp alfa (in weeks) during the study is defined as:

$$\text{Duration of treatment} = \left( \frac{\text{date of last dose} - \text{date of first dose} + 14}{7} \right)$$

The **cumulative dose** of bintrafusp alfa per participant in a time period is the sum of the actual dose that the participants received within that period (i.e., total dose administered (mg)).

The **dose intensity** of treatment (DI) (mg/cycle) of bintrafusp alfa per 2-week/cycle is defined as

$$\text{DI of treatment} = \left( \frac{\text{Cumulative dose of treatment (mg)}}{\text{Duration of bintrafusp alfa of treatment (in weeks)}/2} \right)$$

The **relative dose intensity** (RDI) is defined as the actual dose intensity divided by the planned dose intensity per cycle and expressed in percentage:

$$\text{RDI of treatment (\%)} = 100 \times \left( \frac{\text{DI of treatment (mg/cycle)}}{\text{planned dose level (mg/cycle)}} \right)$$

The following summary tables will be provided:

- Duration of therapy (weeks)

- Total number of infusions received
- Cumulative dose (mg)
- Dose intensity (mg/cycle)
- Relative dose intensity (%) as continue variable, and categorized as
  - < 80%
  - 80%-90%
  - >90%

Two listings will be presented:

- A listing of study intervention which will provide: participant identifier, age, sex, race, visit, infusion start date and time, infusion end date and time, infusion rate (mL/hr), actual dose (mg), route, administration modification and reason for modification, change in administration detail, treatment delay (days). Data collected during the treatment re-initiation phase will be flagged.
- An additional listing of treatment exposure and compliance which will include participant identifier, age, sex, race, duration of therapy (weeks), total number of infusions received, cumulative dose of therapy (mg), dose intensity (mg/cycle), and relative dose intensity (%). For data collected during the treatment re-initiation phase, only the duration of therapy as well as the number of infusions during the re-initiation phase will be summarized.

## Dose Modification

Dose modification is not allowed per protocol. No summaries will be provided.

## Therapy Delays

Delays of therapy will be derived for each infusion as the number of days since last infusion – 14:

Therapy Delays = start date of current infusion – start date of the previous infusion – 14

If the result is >0 day, then this will be classed as a delay. A participant may have more than one treatment delay throughout the course of treatment.

The following will be summarized in a table:

- Number of participants with at least one delay
- Number of participants with no delay
- Number of delays per participant (0 delay, 1 delay, 2 delays, 3 delays,  $\geq$  4 delays)
- Longest delay per participant (no delay, 1-2 days, 3-8 days, 9-15 days,  $\geq$ 16 days)

